8.1.1 Eligibility screening

- For HVs: The investigator or his/her delegate will confirm that the participant fulfills all the inclusion/exclusion criteria

For NEN patients: The Investigator or his/her delegate will contact the registration center after confirming that the participant fulfills all the inclusion/exclusion criteria. The registration center will confirm the result of CIM by central read and notify the registration to investigators. The registration center will limit the enrollment of patients with negative CIM up to 5. Details will be provided in the registration manual.

8.2 Participant demographics/other baseline characteristics

Country-specific regulations should be considered for the collection of demographic and baseline characteristics in alignment with the eCRF.

Participant demographics: age, sex, race/predominant ethnicity (if permitted) and relevant medical history/current medical conditions (until date of signature of informed consent) will be recorded in the eCRF. Where possible, the diagnosis and not symptoms should be recorded. Participant race/ethnicity data are collected and analyzed to identify any differences in the safety and/or efficacy profile of the treatment due to these characteristics. In addition, we will assess the diversity of the study population as required by Health Authorities.

All prescription medications, over-the-counter drugs and significant non-drug therapies prior to the start of the study must be documented. See protocol [Section 10.1.5](#) for further details on what information must be recorded on the appropriate page of the eCRF.

Participant demographic and baseline characteristic data to be assessed on all participants include:

- Demographic information: Age, Gender, Race and ethnicity
- ECOG Performance status scale
- Height and Weight
- Vital signs: Body temperature, Blood pressure, Pulse rate, Respiratory rate measurements
- 12 Lead ECG
- Laboratory evaluations: Hematology, Chemistry, Urinalysis, Coagulation, and Pregnancy testing (if applicable)
- Conventional Imaging (Patients with NENs only)
- Patient Management Questionnaire (Patients with NENs only)
- Adverse Events
- Medical history:
 - Ongoing medical conditions, symptoms and diseases which are recorded on the Medical History eCRF should include the toxicity grade when applicable.
 - Concomitant medications of the last 30 days prior to imaging day

- Other important medical, surgical, and allergic conditions that could have an impact on the participant's evaluation, and current medical conditions (e.g. all relevant current medical conditions which are present at the time of signing informed consent).
- Diagnosis and Extent of Cancer (if applicable for patients with NENs): Date of initial diagnosis, Date of the last relapse/progression, Extent of disease, Functional test, Histopathology result (Diagnosis of disease, Ki67 proliferation index, Histological grade, SSTR expression status). Any assessments after biopsy will be documented on the appropriate eCRF.
- Prior Antineoplastic Medications/Radiotherapy/Surgery

ECOG Performance status scale will be used as described in [Table 8-1](#).

Table 8-1 ECOG performance status

0	Fully active, able to carry on all pre-disease performance without restriction
1	Restricted in physically strenuous activity but ambulatory and able to carry out work of a light or sedentary nature e.g., light house work, office work
2	Ambulatory and capable of all self-care but unable to carry out any work activities. Up and about more than 50% of waking hours
3	Capable of only limited self-care, confined to bed or chair more than 50% of waking hours
4	Completely disabled. Cannot carry on any self-care. Totally confined to bed or chair
5	Dead

8.3 Efficacy assessments

Efficacy assessments in this study include diagnostic assessment of disease using CIM (NENs patients only) at screening as well as assessments of [⁶⁸Ga]Ga-DOTA-TATE PET/CT imaging. In addition, disease assessment using histopathology will be collected for the participants whose histopathology assessment is available. Planned time points for all efficacy assessments are provided in Section 1.3 Schedule of Activities.

8.3.1 Imaging for tumor assessment

The imaging assessment collection plan for this study is presented in [Table 8-2](#).

Table 8-2 Imaging Assessment Collection Plan

Imaging procedure	Mandatory or Optional	Imaging Acquisition Timing
[¹¹¹ In]In-Pentetreotide SPECT/CT**	Mandatory - NENs patients only	screening*
High Resolution CT with contrasts (or MRI if CT with contrast is medically	Mandatory - NENs patients only	screening*

Imaging procedure	Mandatory or Optional	Imaging Acquisition Timing
contraindicated) of at least Chest, Abdomen and Pelvis (and any additional region as clinically indicated)		
[⁶⁸ Ga]Ga-DOTA-TATE PET/CT	Mandatory - all participants	Imaging day

*CIM assessment performed as a part of clinical practice within 2 months prior to imaging day, even before informed consent, can be used as long as imaging quality meets study defined criteria.

**If SPECT/CT is not available in the clinical site, SPECT can be acceptable.

[⁶⁸Ga]Ga-DOTA-TATE PET/CT imaging

[⁶⁸Ga]Ga-DOTA-TATE PET/CT imaging will be performed for all participants including HVs and PET/CT imaging will be submitted to the designated central CRO for independent central review. Three independent reviewers, who will be blinded to CIM and other patient data collected in clinical database will review PET/CT images. Central read results will not be provided to the treating physician/Clinical Study Investigator. If applicable for histopathology assessments detailed in Section 8.3.2, local read results of [⁶⁸Ga]Ga-DOTA-TATE PET/CT imaging will be used for the assessment.

CIM for NENs patient

CIM for patients with NENs must include [¹¹¹In]In-Pentetreotide SPECT/CT and High Resolution CT with intravenous and oral contrasts (or MRI if CT with contrast is medically contraindicated). A centralized reading of CIM for patients with NENs will be performed by a central independent reader who will be blinded to [⁶⁸Ga]Ga-DOTA-TATE PET/CT imaging results and other patient data collected in clinical database. Further details will be provided in the Imaging Manual.

8.3.2 Histopathology assessments

From prospective biopsy or surgery performed within 30 days after imaging day : In the cases where pathology will be available, histopathology assessments by the local pathologists, who are not blinded to [⁶⁸Ga]Ga-DOTA-TATE PET/CT imaging results, CIM and other patient data collected in clinical database, will be performed as per standard clinical practice, and results are to be provided within 2 weeks of the biopsy or surgery.

From retrospective biopsy performed before imaging day : In case if pathology is available, the result will be collected.

Pathology data collected for histopathology assessments can be documented in eCRF (e.g. Diagnosis and Extent of Cancer).

8.3.3 Appropriateness of imaging assessments

CIM including [¹¹¹In]In-Pentetreotide SPECT/CT and High Resolution CT with contrasts (or MRI if CT with contrast is medically contraindicated) is considered as the SoT to assess the diagnostic performance of [⁶⁸Ga]Ga-DOTA-TATE PET/CT imaging. CIM and [⁶⁸Ga]Ga-DOTA-TATE PET/CT imaging will be read by independent central reviewers, who will be

blinded to patient data (including clinical condition, histopathology and each other imaging result).

Since patients with NENs are often metastatic at the time of diagnosis, it is ethically impossible to make a histological diagnosis by biopsy of all lesions, and since CIM including [¹¹¹In]In-Pentetreotide SPECT/CT and High Resolution CT with contrasts (or MRI if CT with contrast is medically contraindicated) have been established for SSTR-positive NENs, it is considered appropriate to evaluate the diagnostic performance of [⁶⁸Ga]Ga-DOTA-TATE PET/CT imaging using CIM as the SoT.

8.4 Safety assessments

Safety assessments are specified below with [Section 1.3 Schedule of Activities](#) detailing when each assessment is to be performed.

For details on AE collection and reporting, refer to [Section 8.6](#).

As per [Section 4.5](#), during a public health emergency as declared by local or regional authorities i.e. pandemic, epidemic or natural disaster, that limits or prevents on-site study visits, regular phone or virtual calls can occur for safety monitoring and discussion of the participant's health status until it is safe for the participant to visit the site again.

8.4.1 Physical examinations

A complete physical examination will include the examination of general appearance, skin, neck (including thyroid), eyes, ears, nose, throat, lungs, heart, abdomen, back, lymph nodes, extremities, vascular, and neurological. If indicated based on medical history and/or symptoms, rectal, external genitalia, breast, and pelvic exams will be performed.

Height in centimeters (cm) and body weight (to the nearest 0.1 kilogram (kg) in indoor clothing, but without shoes) will be measured as specified in [Table 1-2](#).

Information for all physical examinations must be included in the source documentation at the study site. Clinically relevant findings that are present prior to signing informed consent must be recorded on the appropriate eCRF that captures medical history. Significant findings made after signing informed consent which meet the definition of an adverse event must be recorded as an adverse event.

8.4.2 Vital signs

Vital signs (body temperature, pulse rate, blood pressure (Systolic and diastolic), respiratory rate) will be monitored as per [Section 1.3 Schedule of Activities](#).

8.4.3 Electrocardiograms

Figure 8-1 Timing of study procedures

Single local 12 lead ECGs are collected.

ECGs will be locally collected and evaluated. Interpretation of the tracing must be made by a qualified physician and documented on the appropriate eCRF. ECG tracing should be labeled with the study number, participant initials (where regulations permit), participant number, date and time, and kept in the source documents at the study site. Clinically significant ECG abnormalities present at screening should be reported on the appropriate eCRF. Clinically significant findings must be discussed with Novartis prior enrolling the participant in the study. New or worsened clinically significant findings occurring after informed consent must be recorded as adverse events.

The original ECG appropriately signed must be collected and archived at the study site. If heat sensitive paper is used, a certified copy on non-heat sensitive paper must be also collected and archived at the study site.

Additional, unscheduled, safety ECGs may be repeated at the discretion of the Investigator at any time during the study as clinically indicated.

Table 8-3 Local ECG collection plan

Week (or Cycle)	Day	Time	Number of ECG Replicates
Screening	-35 to -1	Screening	12 Lead Single
Imaging day	1	Post dose 2 hours	12 Lead Single
Unscheduled or Unplanned sample		Anytime	12 Lead Single

8.4.3.1 Cardiac imaging - MRA (magnetic resonance angiography), MUGA (multiple gated acquisition) scan or echocardiogram

Not applicable.

8.4.3.2 Cardiac enzymes

Not applicable.

8.4.4 Clinical safety laboratory tests

Local laboratory will be used for analysis of hematology, chemistry, urinalysis, coagulation, and pregnancy testing (if applicable) according to the schedule of assessments as described in [Table 1-2](#). The samples need to be taken prior to the injection of the [⁶⁸Ga]Ga-DOTA-TATE.

Urine samples will be collected at screening, at imaging day and safety follow-up by dipstick and analyzed locally at the clinical site if dipstick results are abnormal.

All abnormal lab results must be evaluated for criteria defining an adverse event and reported as such if the criteria are met. For those lab adverse events, repeated evaluations are mandatory until normalization of the result(s) or until the result is no longer considered to be clinically significant.

Abnormal laboratory values or test results constitute adverse events only if they fulfill at least one of the following criteria: 1) they induce clinical signs or symptoms, 2) they are considered clinically significant, or 3) they require concomitant therapy or procedures. Clinically significant abnormal laboratory values or test results should be identified through a review of values outside of normal ranges/clinically notable ranges, significant changes from screening or the previous visit.

At any time during the study, abnormal laboratory parameters which are clinically relevant, whether specifically requested in the protocol or not, will be recorded on the AE eCRF page. Laboratory data will be summarized using the Common Terminology Criteria for Adverse Events (CTCAE) version 5.0 ([Section 10.3.1](#)). Additional analyses are left to the discretion of the Investigator.

Novartis must be provided with a copy of the local laboratory's certification (if applicable), and a tabulation of the normal ranges and units of each parameter collected in the eCRF. Any changes regarding normal ranges and units for laboratory values assessed during the study must be reported via an updated tabulation indicating the date of revalidation.

The Investigator is responsible for reviewing all laboratory reports for participants in the study and evaluating any abnormalities for clinical significance.

Table 8-4 Laboratory assessments

Test Category	Test Name
Hematology	Hematocrit, Hemoglobin, Mean Corpuscular Hemoglobin (MCH), Platelets, Erythrocytes, Leukocytes, Differential (Basophils, Eosinophils, Lymphocytes, Monocytes, Neutrophils (absolute value preferred, percentages are acceptable))
Chemistry	Albumin, Alkaline phosphatase, Alanine Aminotransferase (ALT), Aspartate Aminotransferase (AST), Gamma-glutamyl transferase (GGT), Lactate dehydrogenase (LDH), Bicarbonate*, Calcium, Magnesium, Phosphate (inorganic phosphorus), Chloride, Sodium, Potassium, Creatinine, Creatine kinase (CK), Direct Bilirubin, Total Bilirubin, Blood Urea

Test Category	Test Name
	Nitrogen (BUN) or Urea, Uric Acid, Amylase, Lipase, Plasma Glucose (fasting)
Urinalysis	Macroscopic Panel (Dipstick) (Color, Bilirubin, Blood, Glucose, Ketones, Leukocytes esterase, Nitrite, pH, Protein, Specific Gravity, Urobilinogen) If Dipstick is abnormal, Microscopic Panel (Red Blood Cells, White Blood Cells, Casts, Crystals, Bacteria, Epithelial cells) will be added (only needs to be recorded in the source documentation).
Coagulation	Prothrombin time (PT), International normalized ratio [INR], Activated partial thromboplastin time (APTT)
Pregnancy testing	Serum / Urine pregnancy testing (refer to 'Pregnancy testing' Section 8.4.5)

*Total carbon dioxide or equivalent is acceptable for Bicarbonate

8.4.5 Pregnancy testing

All women of childbearing potential will have pregnancy testing. Serum or urine pregnancy testing depending on Investigator's preference will be performed at screening visit.

A woman is considered of childbearing potential from menarche until becoming post-menopausal unless permanently sterile. A postmenopausal state is defined as no menses for 12 months without an alternative medical cause and an appropriate clinical profile.

Permanent sterilization methods include hysterectomy, bilateral tubal ligation, bilateral salpingectomy and bilateral oophorectomy. In the case of oophorectomy alone, only when the reproductive status of the woman has been confirmed by follow-up hormone level assessment is she considered to be not of child-bearing potential.

Medical documentation of permanent method of sterilization must be retained as source documents.

In absence of the medical documentation confirming permanent sterilization, or if the post-menopausal status is not clear, the Investigator should use his medical judgment to appropriately evaluate the fertility state of the woman and document it in the source document.

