Inclusion / Exclusion criteria	X					
Medical history/current medical conditions	X					
Demography	X					
Diagnosis and Extent of cancer	X ^{1,2}					
Enrollment	X					
Physical Examination	S			S	S	
ECOG performance score	X					
Body Height	X					
Body Weight		X				
Vital Signs	X	X		X	X	
Electrocardiogram (ECG)	X			X		
Hematology	X	X			X	
Clinical Chemistry	X	X			X	
Urinalysis	X	X			X	
Coagulation	X	X			X	
Pregnancy testing (Serum / Urine), if applicable	S					
PK blood collection		X ³		X ³		
[¹¹¹ In]In-Pentetreotide SPECT/CT	X ^{1,4,5}					

Period	Screening	Treatment			Post-Treatment Follow-Up	
Visit Name	Screening	Imaging day			Safety follow up	EOS
Days	-35 to -1	1			8 ±1	30
Time (post-dose)	-	Pre-injection	Injection	Post-injection	-	-
High Resolution CT with contrast (or MRI if CT with contrast is medically contraindicated)	X ^{1,4}					
[⁶⁸ Ga]Ga-DOTA-TATE injection			X			
[⁶⁸ Ga]Ga-DOTA-TATE PET/CT imaging				X ⁶		
Histopathology, if applicable	X ^{1,7}					X ^{1,8}
Patient Management Questionnaire	2 times: Before and until Safety follow up after having the results of the [⁶⁸ Ga]Ga-DOTA-TATE PET/CT imaging assessment in local read of PET/CT imaging. ¹					
Adverse Events	All (S) AE monitoring and (S) AE recording and reporting will begin at the time pf consent and will continue up to 8 days after [⁶⁸ Ga]Ga-DOTA-TATE injection (i.e. Day 9). On and after Day10, SAEs should be reported only if the investigator suspects a causal relationship to study treatment. The presence of study treatment related SAE can be confirmed by phone at EOS.					
Prior/Concomitant Medication	Collected until 8 days after [⁶⁸ Ga]Ga-DOTA-TATE injection (i.e. Day 9). On and after Day10, when the investigator suspects that SAEs are related to study treatment, their relevant medications should be also reported.					
Prior/Concomitant Non-drug therapies	Collected until 8 days after [⁶⁸ Ga]Ga-DOTA-TATE injection (i.e. Day 9). On and after Day10, when the investigator suspects that SAEs are related to study treatment, their relevant therapies should be also reported.					
Prior/Concomitant Non-drug Procedures	Collected until 8 days after [⁶⁸ Ga]Ga-DOTA-TATE injection (i.e. Day 9). On and after Day10, when the investigator suspects that SAEs are related to study treatment, their relevant procedures should be also reported.					
Prior antineoplastic therapy(Medication, Radiation, Surgery)	X ¹					

Period	Screening	Treatment			Post-Treatment Follow-Up	

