4.1 Overall design

Refer to [Section 1.2](#) Schema for study design figure.

This prospective, open-label, multi-center, single arm, phase III study, will enroll approximately 47 adult male or female participants with NENs and 23 HVs. Of all the participants with NENs, the number of participants with suspected NENs is limited to up to 5 with negative CIM by central read in order to enroll sufficient number of participants with positive result in CIM. Negative CIM by central read is applicable for patients who do not show any lesions based on CIM by central read. All eligible participants will undergo [⁶⁸Ga]Ga-DOTA-TATE PET/CT imaging. [⁶⁸Ga]Ga-DOTA-TATE will be administered intravenously at a single dose of 2 MBq/kg (0.054 mCi/kg) of body weight up to a maximum total dose of 200 MBq (5.4 mCi), and imaging will be acquired 40 to 90 minutes after the intravenous injection of [⁶⁸Ga]Ga-DOTA-TATE.

The purpose of this study is to evaluate the diagnostic performance of [⁶⁸Ga]Ga-DOTA-TATE PET/CT imaging compared with the CIM as standard of truth in patients with NENs and HVs. The data from this study will provide the evidence for diagnosis use of [⁶⁸Ga]Ga-DOTA-TATE PET/CT imaging in patient with NENs in Japan.

Screening

Participants must sign an informed consent form (ICF) prior to any study specific screening evaluations. All screening procedures must be completed within 35 days prior to Imaging day. All procedures described in the Assessment Schedule [Table 1-2](#) must be carried out to confirm the eligibility.

Enrollment

Until Imaging day in the Treatment period, all participants will be assessed for eligibility. Enrollment will take place when all eligibility requirements described in the Assessment Schedule Table 1-2 are confirmed, prior to Imaging day in the Treatment period. After the registration, the tests which are defined in the Table 1-2 as pre-injection should be performed. To calculate the volume of the medication, the weight should be measured. All enrolled participants will be administered intravenously at a dose of 2 MBq/kg (0.054 mCi/kg) of body weight up to a maximum total dose of 200 MBq (5.4 mCi). And after 40-90 minutes from the injection, the participants will undergo $[^{68}\text{Ga}]\text{Ga}\text{-DOTA-TATE}$ PET/CT imaging. This visit should be completed within one day.

Post-Treatment Follow-Up

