The date of the new informed consent signature must be entered on the informed consent eCRF to correspond to the new screening subject number. For re-screening, all screening assessments must be performed per protocol.

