8.1 Screening

Screening

Written informed consent must be obtained prior to any screening procedures. Please refer to [Section 10.1.2](#) for the Informed Consent procedures.

All screening assessments should occur within 35 days prior to imaging day. CIM assessment performed as a part of clinical practice within 2 months prior to imaging day even before informed consent, can be used as standard reference as long as imaging quality meets study defined criteria. Refer to Imaging Manual for details.

It is permissible to re-screen (only once) a participant if he or she fails the initial screening (screen failure); however, each case must be discussed and agreed with the Sponsor on a case-by-case basis. Re-screening should not be performed for avoiding the eligibility criteria, putting the participant at safety risk. Re-screened participants will need to be re-consented and a new Participant Number will be assigned. Re-screening tests should be repeated as per

inclusion/exclusion requirements and re-screening should be documented in the source documents.

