2.1.1 General definitions

Study treatment/ drug

Study treatment/ drug is [⁶⁸Ga]Ga-DOTA-TATE administered intravenously at a dose of 2 MBq/kg (0.054 mCi/kg) of body weight up to a total maximum dose of 200 MBq (5.4 mCi) even if no [⁶⁸Ga]Ga-DOTA-TATE PET/CT scan was acquired.

Study day

The study day describes the day of the event or assessment date, relative to the reference start date.

The study day is defined as:

- The date of the event (visit date, onset date of an event, assessment date etc.) – reference start date + 1 if event is on or after the reference start date;
- The date of the event (visit date, onset date of an event, assessment date etc.) – reference start date if event precedes the reference start date.

The reference date for all assessments is the start of study treatment.

The study day will be displayed in the data listings. If an event starts before the reference start date, the study day displayed on the listing will be negative.

Time unit

A year length is defined as 365.25 days. A month length is 30.4375 days (365.25/12). If duration is reported in months, duration in days will be divided by 30.4375. If duration is reported in years, duration in days will be divided by 365.25.

Baseline

The last available assessment including unscheduled assessments before injection of study drug is taken as “baseline” value or “baseline” assessment.

If participants have no value as defined above, the baseline result will be missing.

On-treatment assessment/event and observation periods

The overall observation period will be divided into three mutually exclusive segments:

1. Pre-treatment period: from day of participant’s informed consent to the day before dosing of investigational drug.
2. On-treatment period: from day of dosing of investigational drug to 8 days after dosing of investigational drug. (i.e. Day 1 – Day 9)
3. Post-treatment period: starting 9 days after dosing of investigational drug. (i.e. start from Day 10)

If dates are incomplete in a way that clear assignment to pre-, on-, post-treatment period cannot be made, then the respective data will be assigned to the on-treatment period.

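### The only pregnancy test the protocol requires can be up to 35 days old when the radioactive tracer is injected

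*Protocol*

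**What the plan says.** Protocol 8.4.5 sets a single test: "Serum or urine pregnancy testing depending on Investigator's preference will be performed at screening visit". In Table 1-2 the row "Pregnancy testing (Serum / Urine), if applicable" has one mark, under screening, coded as source documentation only.

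The only limit on the age of that test is the screening window. Section 4.1 states "All screening procedures must be completed within 35 days prior to Imaging day", and 8.1 repeats it: "All screening assessments should occur within 35 days prior to imaging day". Re-screening starts a new window: "For re-screening, all screening assessments must be performed per protocol" (5.3).

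Enrollment takes place once the eligibility requirements "are confirmed, prior to Imaging day in the Treatment period" (4.1). The same section then says what remains to be done: "After the registration, the tests which are defined in the Table 1-2 as pre-injection should be performed".

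Inclusion criterion 6 asks for a negative urine or blood test without saying how recent it must be. Exclusion criterion 7 bars pregnant participants without naming a test or a time. Section 8.6.4 does not oblige participants to use contraception.

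**The concern.** The protocol excludes pregnant women, so it already treats exposure of a pregnancy to the tracer as something to avoid. The one check that supports this exclusion can be five weeks old at dosing, and nothing in the text guards against conception in the interval. Hematology, chemistry, urinalysis and coagulation are all repeated just before injection, but the pregnancy test is not.

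What is at stake is participant safety: avoidable exposure of an early pregnancy to the tracer and to the CT part of PET/CT, in a study from which participants are not expected to benefit directly (2.3) and which includes healthy volunteers. No estimate, test or sample-size figure depends on this point.

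**Working it through.** The plan gives no figure of its own to reproduce. The check is study-day arithmetic plus a reading of every provision that might force a later test.

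**Age of the test at dosing**
- Inputs: screening runs from Day -35 to Day -1 and dosing is Day 1 (Table 1-2). For dates before dosing, SAP 2.1.1 subtracts the "reference start date if event precedes the reference start date". Dates on or after dosing have 1 added, so there is no Day 0.
- Day -1 is the dosing date minus 1 day: the test is 1 day old.
- Day -35 is the dosing date minus 35 days: the test is 35 days old.
- Range as written: 1 to 35 days. With a Day 1 pre-injection test: 0 days.

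**Tests required on imaging day before injection**
- Table 1-2 marks seven rows in the pre-injection column: body weight, vital signs, hematology, clinical chemistry, urinalysis, coagulation and PK blood collection.
- Pregnancy testing is not among them, and 4.1 ties the tests done after registration to that column.

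**Other provisions that might close the gap**
- 8.4.4 requires laboratory samples to precede injection, following Table 1-2. A Day -35 sample satisfies this.
- 4.1 has eligibility assessed up to imaging day but names no pregnancy recheck.
- Section 8 allows repeat or unscheduled safety samples but does not require them.
- 5.3 repeats the test on re-screening, within another 35-day window.
- The allowance in 8.1 to use scans up to 2 months old covers conventional imaging only and does not lengthen the pregnancy-test window.
- 8.6.4 requires a pregnancy to be reported within 24 hours of its becoming known. That acts after exposure.

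**Size of the exposure (adult effective dose, tracer only)**
- Section 4.3 gives two values for 150 MBq in a 75 kg adult: 3.15 mSv and 3.45 mSv.
- Per unit activity: 3.15 / 150 = 0.021 mSv/MBq and 3.45 / 150 = 0.023 mSv/MBq.
- At the 200 MBq cap, assuming linear scaling: 0.021 × 200 = 4.2 mSv and 0.023 × 200 = 4.6 mSv. At 2 MBq/kg the cap is reached only at 200 / 2 = 100 kg or more.
- For an assumed body weight of 50 kg: 2 × 50 = 100 MBq, giving 2.1 to 2.3 mSv.

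**The case against.** The strongest reply is that no passage conflicts with another and no harm has been shown. About 70 participants are planned, and the number who could become pregnant is not stated. The expected number of exposures prevented could be close to zero, and a same-day test can still miss a very early conception. Section 4.3 describes the radiation effect as minimal, which is consistent with a deliberate risk position. Section 6.2 requires preparation and administration to follow radiation safety rules that are not reproduced in the protocol, and 6.8.2 permits oral or injectable contraceptives in female healthy volunteers. For patients, the larger tracer dose quoted in 4.3 is the 13 mSv from indium-111 pentetreotide. That scan falls in screening or earlier, where a Day 1 test does nothing. Finally, the SAP amendment is dated September 2024, so few women may be left to benefit.

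Most of this limits the benefit and does not remove the gap. The benefit is unquantified, and the fix addresses only the gallium-68 injection and its PET/CT. The consent form, Investigator's Brochure, Pharmacy Manual and registration manual were not available and may advise a check. But permitting contraception does not require it, and a general duty to follow radiation rules does not schedule a test. The case for change rests on the protocol's own exclusion of pregnant women and on the low cost of enforcing it at the time of dosing.

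**Conclusion.** The concern holds. The only mandated pregnancy test is 1 to 35 days old at injection, and no provision in the protocol or SAP compels a later one. This follows directly from Table 1-2, 4.1 and 8.4.5 and needs no assumption beyond the SAP's study-day convention.

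The dose figures are adult effective doses for the tracer alone. They assume linear scaling with activity, exclude CT and should not be read as fetal doses. No expected number of exposures can be given. This is a recommended safety improvement and leaves the co-primary analyses as they are.

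**What to change.** Mark pregnancy testing, for women of childbearing potential, in the imaging-day pre-injection column of Table 1-2. State in 8.4.5 that a negative result from that test is required before injection. Use the urine already collected that day (8.4.4), or serum if the result is back in time. Keep inclusion criterion 6 as the screening test, because enrollment is completed before imaging day. A woman who tests positive on Day 1 is not dosed and is handled as an early terminator under 5.3.

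Costs:
- A written amendment with sponsor and IRB/IEC approval, and health authority approval where required (10.1.8.1). Only women dosed afterwards benefit. No participants were enrolled when Amendment 1 (November 2023) was released; enrollment after that is not stated.
- One strip or assay per woman concerned. There is no new visit, invasive procedure or database field, since the result stays in source documents.
- If a test is positive, the pregnancy consent, reporting and follow-up in 8.6.4 apply, as they do whenever a pregnancy after consent becomes known.
- An undosed woman would be in the FAS but not the EFF. Section 5.3.1 rules out replacement, but 9.9.1 continues enrollment until the EFF reaches 70. As SAP 2.5.6 is worded, she would enter the all-positive and all-negative supplementary analyses, which run only if both co-primary objectives are met. Protocol 9.3.7 describes those analyses more narrowly, for PET/CT images that are not evaluable, so the team should confirm which applies.
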